4.4. Other Efficacy Endpoint Analyses

CCI

CCI

CCI

CCI

CCI

CCI

CCI

CCI

4.7. Safety Analyses

The safety analyses will be based on the full analysis set, unless otherwise specified.

4.7.1. Extent of Exposure

Summary statistics and a categorical overview will be generated for the number of study interventions administered.

The number of days of exposure (therapeutic coverage) to study drug will be calculated based on the formula:

$$\begin{aligned} & \text{Duration of exposure in days} \\ &= \text{Date of last dose of study treatment} - \text{date of first dose of study treatment} \\ &+ 29. \end{aligned}$$

Exposure in months will be calculated using the formula:

$$\text{Exposure (months)} = \left(\frac{\text{Exposure in days}}{365.25} \right) * 12$$

Total participant years exposure will be calculated using the formula:

$$\text{Total participant-years exposure} = (\text{Sum across participants of exposure in days})/365.25$$

The extent of exposure (in months) to mepolizumab will be summarised by treatment group. The number and percentage of participants exposed for 1 to 3 months, 3 to 6 months, 6 to 9 months and 9 to 12 months will be presented. The total participant-years exposure will also be presented.

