4. STUDY DESIGN

4.1. Overall Design

This is a 52-week, open-label, single arm, multicentre study of mepolizumab SC in children and adolescent participants with HES receiving SoC therapy.

Participants will be aged 6 to 17 years at Screening (Visit 1) and are expected to remain in the study for 52 weeks. Approximately 15 participants who are on a stable dose of HES therapy for at least 4 weeks prior to Visit 2 will be enrolled. Participants will have a 2- to 4-week run-in period for training and compliance on the use of their eDiary to record daily assessments. Eligible participants will receive the first dose of mepolizumab at Visit 2.

All participants will need to attend a study-site visit at Screening (Visit 1), Baseline (Visit 2), Week 4 (Visit 3), Week 8 (Visit 4), Week 24 (Visit 8), and the Week 52 exit visit (Visit 15). The other visits may be performed remotely where applicable country and local regulations allow. Home healthcare services may also be utilised to support these activities where local regulations and infrastructure allow. The last dose of mepolizumab will be given at Week 48 and the final visit of the treatment period will be at Week 52. There is a follow-up visit 8 weeks after the Week 52 visit (12 weeks after the last dose of mepolizumab). Protocol-defined eligible participants may enter an EAP, where available, immediately after completion of the 52-week study period (Section 6.6). Participants who enter the EAP will not need a study follow-up visit.

All participants will be on active treatment with mepolizumab. Investigators may adjust HES therapy (SoC) as needed from Visit 3 (4 weeks after the first dose of mepolizumab). All participants will be managed during the study according to routine medical care (i.e., participants and/or caregiver will be instructed to contact their investigator for evaluation or seek emergency care as necessary if they or their child experience worsening of symptoms as per their usual practice).

The investigators will use the CCI [REDACTED] to assess for the presence of a HES flare.

An Independent Data Monitoring Committee (IDMC) will be utilised during the study.

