5. STUDY POPULATION

The study will enrol participants aged 6 to 17 years with uncontrolled HES, defined by at least 2 HES flares within the past 12 months and a blood eosinophil count of ≥ 1000 cells/ μ L at Screening.

At least 15 participants will be enrolled and receive at least one dose of mepolizumab. C

CI

Prospective approval of protocol deviations to recruitment and enrolment criteria, also known as protocol waivers or exemptions, is not permitted.

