3. ANALYSIS SETS

Analysis Set	Definition / Criteria	Analyses Evaluated
Screened	
 All participants who were screened for eligibility. 	
 Study Population
Enrolled	
 All participants who entered the study (post screening) for whom a record exists on the study database. 	
 Study Population
Full Analysis Set (FAS)	
 All participants received at least one dose of study treatment (mepolizumab). 	
 Efficacy Safety Pharmacokinetic Pharmacodynamics

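### The exposure bands in SAP 4.7.1 leave out any single-dose participant and any participant whose Week 48 dose is a day or more late

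*SAP*

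**What the plan says.** SAP 4.7.1 sets out the calculation in steps. First, "The number of days of exposure (therapeutic coverage) to study drug will be calculated based on the formula": date of last dose minus date of first dose, plus 29. Then, "Exposure in months will be calculated using the formula": days divided by 365.25, times 12. No rounding rule is given. The section then lists the bands for the categorical display, participants "exposed for 1 to 3 months, 3 to 6 months, 6 to 9 months and 9 to 12 months will be presented". No band lies below 1 month or above 12 months.

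The same section also plans summary statistics and a categorical overview of the number of doses given, a summary of exposure in months by treatment group, and total participant-years.

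SAP 4.7 bases the safety analyses on the full analysis set unless stated otherwise. SAP Section 3 defines that set as "All participants received at least one dose of study treatment (mepolizumab"), so one dose is enough to enter it. On dosing, Protocol 4.1 states: "The last dose of mepolizumab will be given at Week 48 and the final visit of the treatment period will be at Week 52". Table 1 of the protocol (Schedule of Activities) allows 7 days either side of the Week 48 visit. Protocol Section 5 gives the size of the study: "At least 15 participants will be enrolled and receive at least one dose of mepolizumab".

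**The concern.** A table of counts and percentages by duration should place each member of its analysis set in exactly one row. Here the upper limit of the top band sits almost exactly at the length of a full course, so an ordinary, protocol-compliant delay of one day at Week 48 takes a participant out of the table. At the other end, the 29 days credited for a single dose fall short of one month, so a participant who stops after the first dose has no row either.

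At stake is whether the displayed counts add up to the full analysis set. With about 15 participants, shown by treatment group as well as overall, one or two people without a row would be visible. They would come from the two ends of the exposure range, where a safety reader is likely to look. The programmer would have to choose a rule that the SAP does not give.

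**Working it through.** The documents state no expected count per band, so there is no figure of the plan's own to reproduce. The check applies the SAP formula to the dosing schedule.

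**Inputs**
- Days of exposure = (last dose date − first dose date) + 29; months = days / 365.25 × 12 (SAP 4.7.1).
- Bands: 1–3, 3–6, 6–9 and 9–12 months (SAP 4.7.1).
- Nominal last dose: Week 48 = 48 × 7 = 336 days after the first dose (Protocol 4.1).
- Permitted window at Week 48: ±7 days (Protocol Table 1), read here as relative to the date of the first dose.
- Not in the documents: when within the window doses are actually given.

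**Limits in days.** One month is 365.25 / 12 = 30.4375 days, so 12 months is 365.25 days. Exposure is a whole number of days. A value is therefore above the top band from 366 days, and below the lowest band up to 30 days.

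**Results**

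| Case | Days | Months | Band |
|---|---|---|---|
| One dose only | 0 + 29 = 29 | 0.95 | none |
| Two doses | 28 + 29 = 57 | 1.87 | 1–3 |
| Week 48 dose 7 days early | 329 + 29 = 358 | 11.76 | 9–12 |
| Week 48 dose on the nominal day | 336 + 29 = 365 | 11.99 | 9–12 |
| Week 48 dose 1 day late | 337 + 29 = 366 | 12.02 | none |
| Week 48 dose 7 days late | 343 + 29 = 372 | 12.22 | none |

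A last dose on any nominal dosing day from Week 4 to Week 48 falls in a band.

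**Share of full-course participants affected.** This depends wholly on the dosing dates, so it needs an assumption:
- Even spread over the 15 possible days from −7 to +7: 7 of 15 days are late, 7/15 = 47%. If all 15 participants completed treatment, that would be about 7 people.
- Truncated normal delay, SD 1 to 4 days, centred on the nominal day: 30% to 45%.
- The same, centred 2 days early: 0% to 28%.
- The same, centred 3 days late: 70% to 100%.
- Logical range: 0% to 100%.

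**Would rounding close the gaps?** Rounding to whole months would take 0.95 to 1 and 12.02–12.22 to 12, so both end gaps close. But the shared limits would then matter. A last dose at Week 8 (56 + 29 = 85 days, 2.79 months) becomes 3, one at Week 20 (140 + 29 = 169 days, 5.55 months) becomes 6, and one at Week 36 (252 + 29 = 281 days, 9.23 months) becomes 9. Each of these sits in two bands. Rounding to one decimal takes 0.95 to 1.0 and a one-day delay to 12.0, but two days late (367 days, 12.06 months) becomes 12.1 and is still outside.

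**The case against.** The strongest reply is that nothing of substance is lost. Everyone stays in the exposure analysis. The summary of exposure in months shows the minimum and maximum by default (SAP 4.1.1), the dose-count overview shows who had one dose and who had all of them, and SAP 6.1.1 summarises completion and discontinuation of treatment. This stands, and it limits the point to the one set of rows.

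It can also be said that the single-dose case is hypothetical, since nothing in the documents suggests that anyone will stop after one dose. That is fair, but the analysis set admits such a participant and a table rule should provide for one. The late Week 48 dose needs no unusual event at all.

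A third reply is that the bands are only labels and a rounding convention is understood. The SAP states none, and whole-month rounding would exchange the gaps for overlaps.

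Three stronger readings are tempting, and the documents support none of them:
- *About half of completers drop out of the table.* The 47% rests on an even spread of dosing dates. The protocol gives only the permitted window, and a participant dosed on schedule is covered.
- *Participants are counted twice at 3, 6 and 9 months.* Those limits equal 91.3125, 182.625 and 273.9375 days. Exposure is a whole number of days, so without rounding no one can fall on them.
- *The denominators for the safety data are wrong.* Adverse event percentages use the full analysis set, and participant-years come from the sum of exposure days. Neither uses the bands.

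**Conclusion.** The point holds as a minor error in a stated rule. Applied as written, the bands in SAP 4.7.1 do not cover the full analysis set. Any single-dose participant (0.95 months) and any participant whose Week 48 dose is 1 to 7 days late within the window (12.02 to 12.22 months) have no row. This follows from the SAP's formula and the protocol's schedule, with months left unrounded. How many people are affected cannot be known from the documents, and any percentage is conditional on assumed dosing dates.

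The consequence is that one descriptive table may fail to add up to the analysis set. The summary statistics for exposure, like the primary flare analysis and the other safety results, do not change.

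**What to change.** In SAP 4.7.1, replace the four bands with <3, 3 to <6, 6 to <9 and ≥9 months, applied to unrounded months. Every possible value then falls in exactly one band: a single dose goes to <3, and a full course anywhere in the Week 48 window (11.76 to 12.22 months) goes to ≥9. The top band will also hold participants whose last dose was as early as Week 36 (9.23 months on the nominal day). Full-course completion should therefore be read from the dose-count summary already planned, where a full course is 13 doses (48 / 4 + 1).

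The cost is a one-line SAP edit and the matching row labels in one table. No new data, analysis or protocol change is needed.

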4.7.2. Adverse Events

Summary of adverse events (AEs), Serious (SAEs) and other significant AEs will be based on GSK Core Data Standards. AEs will be summarised for all participants by treatment group and overall.

4.7.2.1. Adverse Events of Special Interest

Adverse events of special interest (AESIs) reported by the investigator as systemic reactions (further categorised by the investigator as either allergic [type I hypersensitivity] or other systemic reactions and assessed against Sampson criteria for anaphylaxis) are collected via targeted eCRF within the study. Local injection site reactions are also collected via targeted eCRF within the study.

AESIs of opportunistic infections, malignancies, serious cardiac, vascular and thromboembolic (CVT) events and serious ischemic events will be identified from a list of relevant preferred terms maintained within a project level reference dataset created based on the MedDRA dictionary available at the time of Database Lock for this study. In addition, the information as to whether an event met the diagnostic criteria for anaphylaxis as outlined by the Second Symposium on Anaphylaxis [[Sampson, 2006](#)] will be collected on the AE and SAE eCRF pages. See Appendix 4 (Section [6.4](#)) for further details.

Separate summary tables showing the number and percent of participants with each type of AESI, broken down by preferred term will be created.

For each type of AESI a profile summary table will be produced containing information including, but not limited to, the number of occurrences of the event, event characteristics, time to onset, intensity, outcome and action taken.

4.7.2.2. COVID-19 AEs

The COVID-19 will be reported as part of AE/SAE tables, listings and figures.

4.7.3. Additional Safety Assessments

The analyses of non-laboratory safety test results including ECGs and vital signs will be based on GSK Core Data Standards, unless otherwise specified.

4.7.3.1. Laboratory Data

Laboratory evaluations including the analyses of Chemistry laboratory tests, Urinalysis, Haematology laboratory tests and liver function tests will be based on GSK Core Data Standards.

A scatter plot of maximum ALT vs baseline ALT, and maximum ALT vs total bilirubin will be produced. In addition, if any liver stopping or liver monitoring events occur during the study, summaries of liver monitoring/stopping event reporting and hepatobiliary laboratory abnormalities will be produced.

4.7.3.2. Height, Weight and Vital signs

A summary of the vital signs data (height, weight, temperature, systolic and diastolic blood pressure, and heart rate) will be produced by test, treatment group and visit. A summary of change from baseline in vital signs will be also produced.

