1.3. Schedule of Activities (SoA)

The Schedule of Activities (SoA) is presented in [Table 1](#).

CONFIDENTIAL

215360
Protocol Amendment 4 Final

Table 1 Schedule of Activities

Procedures	Screen	Treatment Period and Exit Visit ¹															Early discontinuation /Withdrawal Visit		Follow-up
Study visit	1	2	3	4	5	6	7	8	9	10	11	12	13	14	15 Exit visit	Flare ²	Discontinue from study treatment Visit (replacing visits 2-15) ³	Withdrawal Visit	16
Study week	-2 to -4	0	4 (±7 days)	8 (±7 days)	12 (±7 days)	16 (±7 days)	20 (±7 days)	24 (±7 days)	28 (±7 days)	32 (±7 days)	36 (±7 days)	40 (±7 days)	44 (±7 days)	48 (±7 days)	52 (±7 days)				~12 wks After last dose (±7 days)
Informed consent ⁴	X																		
Eligibility assessments																			
Inclusion/Exclusion criteria	X	X																	
Demography/childbearing status assessment	X																		
Medical and treatment history	X																		
Parasite screening ⁵	X																		
Physical examination including height and weight	X							X							X				
Efficacy assessments																			
CCI																			
Concomitant medications including OCS		X	X	X	X	X	X	X	X	X	X	X	X	X	X	X	X	X	X
CCI																			
BFI item 3 ⁶																			
CCI																			

CONFIDENTIAL

215360
Protocol Amendment 4 Final

Procedures	Screen	Treatment Period and Exit Visit ¹															Early discontinuation /Withdrawal Visit		Follow-up
Study visit	1	2	3	4	5	6	7	8	9	10	11	12	13	14	15 Exit visit	Flare ²	Discontinue from study treatment Visit (replacing visits 2-15) ³	Withdrawal Visit	16
Study week	-2 to -4	0	4 (±7 days)	8 (±7 days)	12 (±7 days)	16 (±7 days)	20 (±7 days)	24 (±7 days)	28 (±7 days)	32 (±7 days)	36 (±7 days)	40 (±7 days)	44 (±7 days)	48 (±7 days)	52 (±7 days)				~12 wks After last dose (±7 days)

CCI

Safety assessments

AE/SAE assessment	X ¹¹	X	X	X	X	X	X	X	X	X	X	X	X	X	X	X	X	X	X
Vital signs ¹²	X	X						X							X	X		X	
ECG	X														X	X			

Laboratory assessments¹³

Haematology with differential	X ¹⁴	X	X	X	X	X	X	X	X	X	X	X	X	X	X	X	X	X	
Clinical and liver chemistry	X	X			X			X			X			X		X	X ¹⁵	X	
Pregnancy test ¹⁶	X	X	X	X	X	X	X	X	X	X	X	X	X	X	X		X ¹⁷	X	X
Urinalysis ¹⁸	X														X		X ¹⁵	X	
Hepatitis serology ¹⁹	X																		
Total IgE		X																	
F/P status ²⁰	X																		
T-cell profile	X																		
Immunogenicity		X						X							X		X ²¹	X	X
PK sample			X					X							X		X ²²	X	
IL-5		X																	

Investigational product

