The initial response to OCS treatment is often positive; however, long-term use is associated with significant and commonly reported adverse effects in chronic inflammatory conditions [Poetker, 2010]. This is particularly important in paediatric patients who likely have long-term sequelae. Commonly reported adverse effects in children are weight gain, growth retardation, and Cushingoid features, while increased susceptibility to infection was the most serious adverse drug reaction [Aljebab, 2017]. Therefore, with chronic use, the toxicities of OCS therapy diminish patient adherence to treatment, which may increase the risk of worsening symptoms and/or increased blood eosinophils [Roufosse, 2013].

As described herein, due to the significant tolerability issues related to long-term use of corticosteroids and other chemotherapeutics, new alternative therapies with a positive risk/benefit profile are needed.

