8.2.1. Physical Examinations

Height and weight will be measured using a calibrated stadiometer (appropriate for the participant's age) and plotted on age and gender appropriate charts so that a visual assessment can be performed relative to normative standards for height and weight and change in height and weight over time (Section [10.13](#)).

A complete physical examination will include, at a minimum, assessments of the ENT, Skin, Cardiovascular, Respiratory, Gastrointestinal and Neurological systems. Height and weight will also be measured and recorded.

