4.1.1. General Methodology

Confidence intervals will use 95% confidence levels unless otherwise specified.

Unless otherwise specified, continuous data will be summarized using descriptive statistics: n, mean, standard deviation, median, minimum and maximum. Categorical data will be summarized as the number and percentage of participants in each category.

It is anticipated that participant accrual will be spread thinly across centers and summaries of data by center would unlikely be informative and will not, therefore, be provided.

For the primary analyses, region will be grouped into Europe (Italy, Netherlands, Spain and United Kingdom), United States and Rest of the World (Argentina, Brazil, Israel, Mexico, Russian Federation and Turkey). If the number of participants is too small for model convergence, then the subgroup categories may be redefined prior to database lock for the study.

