4.1.2. Baseline Definition

CCI
CCI
CCI
CCI
CCI
CCI
CCI
CCI
CCI
CCI
CCI
CCI
CCI
CCI
CCI
CCI
CCI
CCI
CCI

For all other endpoints the baseline value will be the latest pre-dose assessment with a non-missing value, including those from unscheduled visits. If time is not collected, Day 1 assessments are assumed to be taken prior to first dose and used as baseline.

Unless otherwise stated, if baseline data is missing no derivation will be performed and baseline will be set to missing.

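### The SAP summarises height and weight unstandardised and lists no output for the comparison with age and sex norms that Protocol 8.2.1 sets up

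*SAP*

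**What the plan says.** **Protocol.** Section 8.2.1 requires height and weight to be "plotted on age and gender appropriate charts so that a visual assessment can be performed relative to normative standards for height and weight", and extends this to "change in height and weight over time", with a reference to Section 10.13. The Schedule of Activities row "Physical examination including height and weight" is marked at Screening, Week 24 and Week 52. Section 2.2 gives the reason for interest in growth when it discusses long-term oral corticosteroids (OCS): "Commonly reported adverse effects in children are weight gain, growth retardation, and Cushingoid features".

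**SAP.** Section 4.7.3.2 states: "A summary of the vital signs data (height, weight, temperature, systolic and diastolic blood pressure, and heart rate) will be produced by test". The same display is broken down by dose group and by visit. The section then adds: "A summary of change from baseline in vital signs will be also produced". By default (4.1.1), "continuous data will be summarized using descriptive statistics: n, mean, standard deviation, median, minimum and maximum". Section 4.9.1 provides safety summaries overall and separately for ages 6 to 11 and 12 to 17. Section 4.1 puts only a minimum set of listings in the study report and leaves other participant-level data in an internal viewer. No visible SAP text mentions a z-score, percentile, growth velocity, reference population or growth chart.

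**The concern.** The protocol sets up a comparison with norms, and the visible SAP does not carry it into a reported result. What the SAP does report is hard to interpret in this population. Children gain height and weight over a year whatever their treatment, and the gain expected depends strongly on age, sex and puberty. With no control arm, an external norm is the only available yardstick.

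The protocol itself names growth retardation and weight gain as harms of the background steroid, and several secondary endpoints concern reducing that steroid. A reader of the study report will want to know whether growth and weight gain over the year were within normal expectation. A table of mean centimetres and kilograms by visit does not say.

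**Working it through.** The documents give no figure for height, weight or growth, so there is nothing to reproduce. The check is a comparison of text, followed by an illustration on assumed values.

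**1. Text side by side**
- Protocol 8.2.1: comparison with age- and sex-specific norms, including over time, by visual assessment of individual charts.
- SAP 4.7.3.2 with 4.1.1: n, mean, SD, median, minimum and maximum of the measured value by visit. Because the section lists height and weight as vital signs data, change from baseline as well. This last step is an inference: the vital-sign safety endpoint in SAP 1.1 names only blood pressure, heart rate and temperature. If that narrower list governs, no change summary for height or weight is visible at all.
- SAP 4.9.1: two age bands, each six years wide.

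**2. What a raw mean change would show under normal growth**
- Age mix: 11 children and 4 adolescents, the stated minimums in the Amendment 4 summary of changes, which add up to the planned 15.
- Assumptions not in the documents: normal growth of 5 to 6 cm/year in children, and 0.5 to 9 cm/year in adolescents depending on pubertal stage.
- Formula: mean = (11 × child rate + 4 × adolescent rate) / 15.
- Low end: (11 × 5 + 4 × 0.5) / 15 = 57 / 15 = 3.8 cm.
- High end: (11 × 6 + 4 × 9) / 15 = 102 / 15 = 6.8 cm.
- With a uniform 1 cm/year deficit: 2.8 to 5.8 cm.

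An observed mean anywhere from 3.8 to 5.8 cm fits either case.

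**3. Sampling error** (95% half-width = t × SD / √n, assumed SD of raw change 1.5 to 3 cm)
- n = 15, t = 2.145: 0.83 to 1.66 cm.
- n = 4 adolescents, t = 3.182: 2.39 to 4.77 cm.

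**4. What the age split does**
On these assumptions the split helps in the younger band, where normal growth is 5 to 6 cm and a 1 cm deficit gives 4 to 5 cm. It does little in the older band, where normal growth alone spans 0.5 to 9 cm and there may be only about four participants. The further split by dose group in 4.7.3.2 makes the cells smaller still.

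**5. Baseline timing**
The visible part of SAP 4.1.2 says: "For all other endpoints the baseline value will be the latest pre-dose assessment with a non-missing value, including those from unscheduled visits". Height and weight are scheduled at Screening and not at Visit 2, so baseline is normally 2 to 4 weeks before the first dose and the Week 52 change spans about 54 to 56 weeks. At 5 to 6 cm/year this adds 5 × 2/52 = 0.19 cm to 6 × 4/52 = 0.46 cm to the raw change. A z-score computed at the exact age on the measurement date allows for this.

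**6. What a z-score change would show**
Its expected value under normal growth is about 0 at any age. With an assumed SD of 0.2 to 0.4, the half-width at n = 15 is 2.145 × 0.2/√15 = 0.11 to 2.145 × 0.4/√15 = 0.22 SD units.

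**The case against.** A reader might infer that the trial cannot tell abnormal from normal growth, or that height and weight are only ever pooled over the whole age range. The documents support neither reading. Protocol 8.2.1 provides an individual comparison with norms, over time, and with about 15 participants a set of charts is a workable way to make that judgement. SAP 4.9.1 also splits safety data by age.

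A reader might also expect z-scores to reveal an effect of mepolizumab on growth. They would not. The study is single-arm and background therapy may be adjusted from Week 4 (Protocol 6.8), so a change could come from mepolizumab, steroid reduction or better disease control.

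Three further points stand in the plan's favour. Growth is in no visible objective, endpoint or estimand, and the mepolizumab risk table in Protocol 2.3.1 does not list it, so the SAP breaks no stated analysis commitment. The Section 10.13 text to which Protocol 8.2.1 refers is not visible because of redaction, and SAP 4.7.3 relies on the sponsor's core data standards, which are not among the documents, so a planned output could exist out of sight. And the growth rates and SDs used above are assumptions.

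These points limit the finding without removing it. On the visible text, the normative comparison is made at the site and reported nowhere, and the summaries that are reported do not replace it.

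**Conclusion.** There is a gap between protocol and SAP. The protocol has height and weight judged against norms, while the visible SAP reports unstandardised values, and by inference their change, overall and in two broad age bands. Those summaries mainly reflect age and pubertal mix. On the assumed rates, normal growth gives a mean gain of 3.8 to 6.8 cm, a range 3 cm wide and so larger than a 1 cm/year deficit. The individual charts can show whether growth was as expected, but no visible output presents them.

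The size is modest. No endpoint or main conclusion of the trial is affected. It is worth acting on because the protocol itself raises growth and weight gain as steroid harms in children, and because the measurements are already scheduled. The conclusion rests on the visible text only; the numbers are illustrative.

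**What to change.** Add to SAP 4.7.3.2 a summary of height-, weight- and BMI-for-age-and-sex z-scores at Screening, Week 24 and Week 52, with change from baseline, overall and in the existing 4.9.1 age groups. Name the reference standard, which should be the one behind the growth charts in Protocol 8.2.1, and compute age at the actual measurement date. State explicitly whether the change-from-baseline summary covers height and weight. Label the output as descriptive, with no attribution to mepolizumab. At a minimum, list the individual growth charts among the study report outputs.

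The cost is SAP wording and a standard reference look-up. Age, sex, height and weight are already collected, and BMI at screening is already summarised under SAP 6.1.2. No new measurement or visit is needed. If a redacted section or the core data standards already provide this, a cross-reference is enough.
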